### 3.1.3 ACCEPTABILITY AND USABILITY

This trial will also explore the features of a smartphone-based dDPP program that are associated with attainment of the primary endpoint in the dDPP arm. The Sweetch dDPP uses a variety of behavioral motivational tools to encourage engagement. We will collect objective (app log data) and subjective (participant questionnaire responses) data to identify the digital health kit components that are most strongly associated with favorable clinical outcomes and/or are perceived to be most useful to participants in promoting engagement (Section 11.11). We hypothesize that the push notifications, digital scale, weight and PA trackers will be perceived to be the most useful features of the digital DPP.

The study will also compare the acceptability of the two interventions with respect to perceived degree of engagement, usefulness, functionality/ease of use, aesthetics, information, and satisfaction (Section 11.10).

### 3.1.4 PREDICTORS OF SUCCESS

This intervention will randomize participants to two fundamentally different approaches for promotion of lifestyle change (fully-automated humanless intervention vs. human coach-based intervention) in adults with prediabetes. As different individuals may respond more favorably to one or the other type of intervention, an objective of this study will be to explore participant characteristics that are associated with successful attainment of the primary endpoint. We hypothesize that younger adults with higher digital skills would respond better to the dDPP, while older adults or those with lower digital skills would respond better to the hDPP given the greater social interaction and lower reliance on technology.

The NPART survey (Evaluation of Non-Participation in Digital Health Research) is a validated instrument that was originally designed to characterize non-participation in digital health research. The survey covers five thematic areas: socioeconomic factors, self-rated health and subjective overall quality of life, social participation, time resources, and digital skills and use of technology. We will use this measure (Section 11.9) as a surrogate marker of need for social interaction (which might be associated with favorable response to the hDPP given human interaction with both lifestyle coach and other participants) and digital skills and technology use (which might be associated with favorable response to the dDPP). We will perform a subgroup analysis among participants in both groups who meet the primary endpoint to evaluate the association between baseline characteristics and NPART scores. Similarly, a subgroup analysis will be done among participants who do not meet the primary endpoint or who fail to engage with either program to identify characteristics associated with low likelihood of success with either intervention. Should this trial demonstrate non-inferiority of the intervention, a screening tool such as the NPART could be used to identify the optimal modality of the DPP for a given patient.

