## 9.4 STATISTICAL ANALYSES

### 9.4.1 GENERAL APPROACH

This clinical trial will be conducted under a common protocol with analyses conducted on pooled data from both sites. Data analyses will be conducted by a biostatistician. Exploratory data analysis will be performed to examine outliers, characterize the distributions of continuous and categorical measures, and track missing data. Mean, median, and frequency counts will be used to summarize baseline characteristics measured on a continuum, and proportions and frequency counts will be used for categorical measures. Baseline statistical differences in continuous measures between groups will be assessed using unpaired t-tests or Wilcoxon signed rank test, and statistical differences in categorical measures will be assessed using chi-square test or Fisher's Exact test as appropriate.

Between-group differences in primary and secondary outcomes will be evaluated in intention-to-treat analyses using mixed effects logistic regression models to account for potential within-program site clustering. For continuous measures in our secondary analyses, linear regression will be used to analyze the outcomes and for binary measures, logistic regression analyses will be used. Interaction terms will be used in regression models to evaluate effect modification.

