#### 9.4.6 WITHIN-GROUP ANALYSES

Several exploratory analyses will be undertaken within the hDPP and DPP arms only to evaluate factors associated with success in either group. In addition, though not a primary focus of this trial, we will conduct a single arm analysis of the hDPP arm only to explore differences in outcomes by study site (JHH vs. Reading), hDPP program site and/or hDPP program type (hospital based, primary care clinic, church, community).

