## 11.9 NPART SURVEY

**NPART Survey (Adapted) (28-item\*)**

The NPART (Evaluation of Non-Participation in Digital Health Research) survey is a validated instrument to characterize non-participation in digital health research. The survey was developed and evaluated in an European population. We have adapted the questions for the U.S. setting. For the purposes of this trial, the results of this survey will not be used to exclude eligible participants. Rather, responses will be analyzed as predictors of responsive to digital vs. in-person DPPs.

What is your current employment status?	 1 Employed. _____ hours per week  0 Not employed, looking for work  0 Not employed, NOT looking for work  0 Retired  0 Disabled, not able to work
What is/was your primary job?*	
Which of the following categories best describes your primary area of employment?	 1 Manager  2 Professionals  3 Technicians and Associate Professionals  4 Clerical Support Workers  5 Services and Sales Workers  6 Skilled Agricultural, Forestry, and Fishery Workers  7 Craft and Related Trade Workers  8 Plants and Machine Operators, and Assemblers  9 Elementary Occupations  10 Armed Forces Occupations  11 I have never worked
Do you have a partner?*	 1 Yes  0 No
Do you live alone?*	 1 Yes  0 No
How often in the past 12 months did you care for a sick or disabled person?	 4 Almost daily  3 Almost every week  2 Almost every month  1 Less often

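### The predictor analyses spelled out in Section 3.1.4 select participants by outcome, so as worded they do not estimate who succeeds or which programme suits whom

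*Combined protocol and SAP*

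**What the plan says.** Section 1.1 lists exploring predictors of success in each programme among the secondary objectives. Section 3.1.4 states the aim as to "explore participant characteristics that are associated with successful attainment of the primary endpoint". It adds a directional hypothesis: "younger adults with higher digital skills would respond better to the dDPP, while older adults or those with lower digital skills would respond better" under the human-coached programme. NPART is to serve as a marker of digital skill and of the need for social contact.

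The analysis then described is a "subgroup analysis among participants in both groups who meet the primary endpoint to evaluate the association between baseline characteristics and NPART scores". The section goes on to say that a "subgroup analysis will be done among participants who do not meet the primary endpoint or who fail to engage with either program", in order to find what marks people unlikely to do well on either programme. It closes by suggesting that, if non-inferiority is shown, "a screening tool such as the NPART could be used to identify the optimal modality of the DPP for a given patient".

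Three other places bear on the same question:

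- Section 9.4.1: "Interaction terms will be used in regression models to evaluate effect modification".
- Section 9.4.6: several "exploratory analyses will be undertaken within the hDPP and DPP arms only to evaluate factors associated with success in either group".
- Section 11.9, on NPART: "responses will be analyzed as predictors of responsive to digital vs. in-person DPPs".

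Sections 9.4.7 and 9.4.8, on the primary and secondary endpoints, set out no predictor or moderator model.

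**The concern.** The hypothesis is an arm-by-characteristic interaction: the effect of dDPP relative to hDPP is expected to change with age and digital skill. Testing it needs success as the outcome, and arm, the characteristic and their product as terms. The first analysis in Section 3.1.4 instead relates two sets of baseline variables to each other among people who all succeeded. The second looks at people who failed or did not engage and states no comparison with those who succeeded.

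At stake is a secondary, exploratory objective. Section 3.1.4 is the only place that specifies a population for the NPART analysis, so an analyst who follows the most specific text would produce results that do not bear on the hypothesis. If the analyst sets that text aside, the moderators and model are left to be chosen after the data are seen.

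**Working it through.** **1. Stated analyses against the objective.**

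- *Successes only.* Success is constant in this subset, so its association with a characteristic cannot be read from the subset alone. The stated association is between baseline characteristics and NPART scores, and arm is not named as a factor.
- *Failures or non-engagers.* No comparison group is stated. Because the subset is defined by failure or non-engagement, a non-engager who meets the endpoint belongs to both subsets. The two are therefore not complements.
- *Section 9.4.1.* Interaction terms are allowed, but no moderator is named and there is no link to this objective.
- *Section 9.4.6.* Factors associated with success are examined within each arm and not only among successes. Separate within-arm results do not test whether an effect differs between arms.
- *Section 11.9.* NPART is called a predictor, without a model or population.

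**2. Does the successes-only association respond to what it is meant to detect?** A simulation of 2,000,000 participants used assumed values throughout: age–skill correlation −0.40, 1:1 arms, and success depending on skill and arm-by-skill only, with an overall rate near 38%. The logistic model was fitted to 200,000 of them.

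| Assumed log odds of success per SD of skill | Age–skill correlation, successes / failures | Mean skill among successes, hDPP / dDPP | All-participant logistic estimates: skill; arm-by-skill |
|---|---|---|---|
| 0 in both arms | −0.398 / −0.399 | 0.00 / 0.00 | 0.00; −0.01 |
| 0.5 in both arms | −0.391 / −0.390 | 0.29 / 0.29 | 0.49; 0.01 |
| −0.3 hDPP, +0.3 dDPP | −0.400 / −0.400 | −0.18 / +0.18 | −0.30; 0.61 |
| 0 hDPP, 0.8 dDPP | −0.395 / −0.394 | 0.00 / 0.43 | 0.00; 0.80 |

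The association described in Section 3.1.4 barely moves across the four cases. The all-participant model recovers the assumed effects; in the third row the true interaction is 0.6.

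**3. Sample size available.** Section 9.2 reproduces. With 50% success in both arms, a 15-point margin, one-sided 5% and 80% power:

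n = 2 × 0.25 × (1.645 + 0.842)² / 0.15² ≈ 137.4, so 138 per arm and 276 in total; 138 / 0.75 = 184 per arm and 368 randomised.

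**4. Power of an all-participant interaction test.** Assume an evenly split binary characteristic, success near 50% in all four cells, and a two-sided 5% test. The difference-in-differences has SE = √(4 × 0.25 / (N/4)) = √(4/N). Power is approximately Φ(difference / SE − 1.96).

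- N = 276: SE = 0.1204. For 20 points, 0.20 / 0.1204 = 1.661, and Φ(−0.299) ≈ 38%. For 15, 30 and 40 points, power is about 24%, 70% and 91%.
- N = 368: SE = 0.1043. For 15, 20, 30 and 40 points, power is about 30%, 48%, 82% and 97%.
- At 35% success, the middle of the range that Section 9.1 expects for hDPP, applied here to both arms with N = 276: SE = √(16 × 0.35 × 0.65 / 276) = 0.1148. Power for 20 points is then Φ(0.20 / 0.1148 − 1.96) ≈ 41%, so the conclusion is the same.

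This is a risk-difference approximation. A logistic interaction is tested on the odds scale.

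**The case against.** Section 3.1.4 is objectives text, and the analysis provisions sit in Section 9. Read with Sections 9.4.1, 9.4.6 and 11.9, the plan does not confine predictor work to outcome-defined subsets. This stands: a reader might infer that predictors are studied only among successes and only among failures, and the documents do not support that.

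A reader might also infer that no analysis restricted to successes could show which programme suits whom, at any sample size. That goes too far. Because arm is randomised, comparing skill between arms among successes is informative about a multiplicative interaction; the simulation shows it (−0.18 against +0.18 under a crossover). Likewise, setting the profiles of successes and failures side by side is an ordinary retrospective comparison that can recover an odds ratio. Section 3.1.4 states neither comparison, and adding non-engagers to the second subset blurs the latter.

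The sentence may also be a drafting slip for the association of baseline characteristics and NPART scores with success. Even so, it is restricted to people who all succeeded.

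Subset size is not a measure of harm. At 30–40% success, 0.30 × 276 ≈ 83 to 0.40 × 276 ≈ 110 participants would be in the first subset, but the other 166–193 would be in the second. The 30–40% is also an expectation for hDPP alone.

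Finally, the closing remark on NPART is speculative. It says what such a tool could do, and no decision rule rests on it.

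**Conclusion.** The point holds in a limited form. The two analyses that Section 3.1.4 spells out are conditioned on outcome. As worded they have neither success as the dependent variable nor arm as a factor, so they do not answer that section's own objective or test its hypothesis. The other provisions point the right way but name no model or moderators, and none replaces or is reconciled with Section 3.1.4.

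The documents do not support reading this as a flaw in the main comparison: the objective is exploratory, and the primary analysis and sample size are unaffected. Nor do they show a commitment to assign patients by NPART.

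The reasoning about the wording needs no numerical assumption. The simulation coefficients, the age–skill correlation and the even split behind the power figures are assumptions, not figures from the plan. With power of about 38% for a 20-point difference-in-differences at N = 276, even the right model would be hypothesis-generating. It would not by itself support choosing a programme by NPART score.

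**What to change.** Replace the two outcome-defined analyses in Section 3.1.4 with one prespecified exploratory model, and refer to it from Sections 9.4.1, 9.4.6 and 11.9:

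- Logistic regression with the primary endpoint as outcome, following the primary analysis population and missing-data handling.
- Terms for arm, age, NPART digital-skills score, NPART social-participation score, and arm-by-age and arm-by-score interactions.
- Predicted success by arm across age and each score, with confidence intervals, labelled exploratory and low-powered.
- A scoring rule for the two NPART scores. Section 11.9 gives item codes but no sub-score scoring, whereas Sections 11.7, 11.10, 11.11 and 11.12 do give scoring rules.

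If a description of non-engagers is still wanted, keep it as a separate descriptive table and do not present it as a predictor analysis.

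The cost is protocol and SAP wording, the scoring definition and a small amount of analysis. Age and NPART are already collected at baseline, so no new data are needed. The drawback is the low interaction power, which the report should state.

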### 3.1.5 FEASIBILITY OF ATTAINING CDC BENCHMARK

The 2021 CDC National Diabetes Prevention Recognition Program benchmark for type 2 diabetes risk reduction, from which the primary endpoint is derived, has not been evaluated in a prospective trial. The CDC has set a benchmark of 60% of program completers meeting the primary endpoint. Few trials have evaluated the effect of the DPP on A1C reduction, which is a new outcome

in the composite primary endpoint. Therefore, a secondary objective of this trial will be to evaluate the feasibility of attaining the 60% benchmark for DPP program completers.

### 3.1.6 VALIDATION OF SELF-REPORTED PHYSICAL ACTIVITY DATA

The primary endpoint includes a PA measure of 150 minutes of PA per week. The CDC accepts self-reported PA data from local DPPs in benchmarking programs for full recognition. Studies have shown that self-reported PA data may be significantly overestimated when compared to objectively measured PA data. A secondary objective of this trial will be to evaluate the correlation between self-reported PA data collected using different methods:

- Data collected and reported by hDPPs
- Self-reported PA data collected by study team obtained at 1 month intervals
- Objectively measured PA data (Actigraphy) obtained at 1 month intervals

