**Secondary Objectives:**

To evaluate the cost-effectiveness of dDPP and hDPPs.

To compare the engagement and rates of program completion of dDPP vs. hDPPs and evaluate whether between-group differences in clinical outcomes are mediated by engagement.

To compare the acceptability and usability of a dDPP vs. hDPPs.

To explore the features of a smartphone-based dDPP program that are associated with attainment of type 2 diabetes risk reduction outcomes.

To explore predictors of success with dDPP and hDPPs.

To evaluate the feasibility of attaining the CDC's National Diabetes Prevention Recognition Program benchmark of 60% of program completers achieving the type 2 diabetes risk reduction outcome.

To validate self-reported physical activity (PA) outcomes among participants in DPP using Actigraphy as a gold standard.

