## 3.3 SECONDARY ENDPOINTS

Secondary endpoints will include:

- Primary endpoint assessed using self-reported PA data in lieu of objectively measured PA data (Actigraphy).
  - In this trial, PA will be assessed using both participant self-reported data and Actigraphy. While the CDC relies on participant self-reported PA data for outcome assessment, in this trial, there is a potential bias introduced from using self-reported PA data alone since the dDPP arm will have access to objective PA data while the hDPP group may or may not (depending on their personal use of wearable devices or fitness tracking apps). Studies have shown over-estimation of PA by self-report. Considering that the CDC accepts self-reported PA data, we

will also analyze results of the primary endpoint using self-reported PA data collected at same interval as serial Actigraphy.

- Change in A1C from baseline to 6 months and 12 months
- Absolute and percentage weight change from baseline to 6 and 12 months
- Changes in physical activity measures (average minutes/week of physical activity, MET-hours per week of physical activity, average number of steps per day) at 6 months and 12 months
- Incident type 2 diabetes (A1C  $\geq 6.5\%$ )
- Engagement level
  - The **dDPP engagement score** will be calculated as the percentage of full weeks during which the app was installed and a) both push notifications and motion sensors were enabled OR b) participant accessed any content within the app.
  - The **hDPP engagement score** will be calculated as a percentage of sessions attended. Per CDC definitions of engagement, the number of required hDPP sessions for months 1-6, 7-12, and 1-12 will be 8, 3, and 11, respectively. For participants who attend more than the required number of sessions across each of these intervals, the engagement score will be capped at 100%. A participant who attends 4 out of 8 sessions in months 1-6 and 1 out of 3 sessions in months 7-12 would receive an engagement score of 50% (4 out of 8 sessions in months 1-6), 33% (1 out 3 sessions in months 7-12), and 45% (5 out of 11 sessions in months 1-12).

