  - Engagement will be analyzed across months 1-6, 7-12, and 1-12 months. For both arms, full weeks will be defined as the number of complete weeks between baseline visit and the 6 month or 12 month visit, respectively. For example, a participant who is followed for 25.4 weeks during months 1-6 and 26.2 weeks during months 7-12 would be considered to have 25 and 26 full weeks on study, respectively.
- Percentage of **program completers**
  - The CDC defines **completers** for the hDPP to be participants who attend at least 8 sessions in months 1-6 and whose time from first session held by the cohort to the last session attended by the participant is at least 9 months. For participants in the hDPP arm, we will evaluate the percentage of completers in the program according to the CDC's definition. Similarly, for the dDPP arm, completers will be defined as participants who meet the engagement definition for at least 8 weeks in months 1-6 AND whose time between app installation and last week of engagement is at least 9 months.
- Acceptability of digital and in-person DPPs
- Correlation of self-reported and objectively measured PA data
- Change in overall well-being scores
- Cost-effectiveness

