#### 9.4.8 ANALYSIS OF THE SECONDARY ENDPOINT(S)

Secondary endpoints will also be analyzed according to the ITT principle. Each of the individual outcomes in the CDC's benchmark for type 2 diabetes risk reduction (a composite endpoint) will be analyzed as a secondary endpoint at both the 6- and 12-month time points. As with the primary effectiveness endpoint, each outcome will be analyzed using logistic regression models. In addition, we will analyze change in A1C, absolute weight change and percentage weight change as continuous measures using linear regression models. Various physical activity measures will be analyzed as continuous measures, including average minutes/week of PA (light, moderate, intense), MET-hours per week of PA, and average number of steps per day. For responses from acceptability questionnaire (Likert-scale questions), non-parametric tests such as Spearman's correlation or chi-square test for independence will be used. For overall Likert scale scores, parametric tests such as Pearson's correlation or t-test will be used.

We anticipate that there will be a very low amount of missing data for the outcomes of A1C and weight for study completers, since both measures are collected by the research coordinator at the study visits. However, since the outcome of PA measurement relies on participants to wear the ActiGraph devices at 1-month intervals, there may be more missing data for this outcome variable. If more than 5% of data for this outcome variable is missing, the primary analysis will be based on multiple imputation. A sensitivity analysis will also be done using a complete case analysis (i.e. participants with 100% of valid PA data) and if results differ significantly, the primary analysis will be interpreted in light of results from the sensitivity analysis.

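### Correlation, the only statistic named for validating self-reported activity against Actigraphy, cannot show the over-reporting that prompts the validation

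*Combined protocol and SAP*

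**What the plan says.** The synopsis lists this secondary objective: "To validate self-reported physical activity (PA) outcomes among participants in DPP using Actigraphy as a gold standard". Section 3.1.6 gives the reason. The CDC accepts self-reported activity when it benchmarks programs, yet "Studies have shown that self-reported PA data may be significantly overestimated when compared to objectively measured PA data". The method follows: "A secondary objective of this trial will be to evaluate the correlation between self-reported PA data collected using different methods". Three sources are listed: minutes reported by the hDPPs, the study team's monthly survey, and monthly Actigraphy.

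Section 3.3 names the endpoint as "Correlation of self-reported and objectively measured PA data". The same section warns that "there is a potential bias introduced from using self-reported PA data alone since the dDPP arm will have access to objective PA data", whereas hDPP participants may or may not have such data. It also plans a repeat of the primary endpoint with self-reported activity in place of Actigraphy.

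Section 9 gives no method for the validation objective. Section 9.4.8 analyzes activity measures as continuous outcomes, and its Spearman and Pearson wording belongs to the acceptability questionnaire.

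Three details affect any paired comparison:
- The survey (Sections 8.2.4 and 11.6) asks for moderate or brisk minutes. The Actigraphy criterion in Section 3.2 states no intensity, and Section 9.4.8 lists light, moderate and intense activity.
- Section 8.2.4 sends the survey 7 days after each scheduled Actigraph assessment. Section 11.6 places it in the week before the measurement.
- Section 8.2.4 accepts that some self-reports will cover a week in which the device was not worn.

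**The concern.** The problem the protocol names is one of level: people may report more minutes than they do. Ordinary correlation describes how closely two measures rise and fall together and carries no information about level. If every participant doubled their minutes, it would not move.

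At stake is what the trial can say about self-report, which Section 3.1.6 notes is the form of data the CDC accepts. If the self-report and Actigraphy versions of the primary endpoint differ, the plan also has no estimate of reporting error, overall or by arm, with which to explain the difference.

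**Working it through.** **What the plan gives.** It states no figure for this objective. The only usable number is the analyzable sample in Section 9.2, which reproduces: n per arm = (1.645 + 0.842)² × (0.5×0.5 + 0.5×0.5) / 0.15² = 6.18 × 0.5 / 0.0225 ≈ 137.4, so 138; and 138 / 0.75 = 184.

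**Invariance.** For self-report S and Actigraphy A, with b > 0, corr(a + bS, A) = b·cov(S, A) / (b·SD(S)·SD(A)) = corr(S, A). Spearman depends on ranks alone, so it is unchanged by any increasing transformation of S. This needs no assumption about the data.

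**Illustration (all parameters assumed).** Actigraphy has a gamma distribution with mean 135 and SD 90 minutes/week, and reporting noise is normal with SD 60. Then r = 90 / √(90² + 60²) = 90 / 108.2 = 0.83. Self-report is then shifted or multiplied. Mean bias is the added constant, or (factor − 1) × 135. Concordance is 2·cov / (var S + var A + bias²). Shares and concordance come from 200,000 simulated participants; 35% reach 150 minutes by Actigraphy.

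| Self-report | r | Mean bias (min/week) | Concordance | At or above 150 by self-report |
|---|---|---|---|---|
| No bias | 0.83 | 0 | 0.82 | 39% |
| Plus 60 minutes | 0.83 | 60 | 0.69 | 63% |
| Times 1.5 | 0.83 | 67 | 0.62 | 59% |
| Times 2 | 0.83 | 135 | 0.44 | 69% |

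An arm with no over-reporting and an arm that doubles its minutes would show the same r.

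**Second set of assumptions.** Actigraphy is log-normal with median 100 and log SD 0.7; reporting noise has log SD 0.4.
- r = √[(e^0.49 − 1)/(e^0.65 − 1)] = √(0.632/0.916) = 0.83 for any factor k.
- Mean Actigraphy is 100·e^0.245 = 127.8, and mean self-report is k × 127.8 × e^0.08 = k × 138.4.
- For k = 1, 1.5 and 2, mean over-reporting is 11, 80 and 149 minutes/week. It is 11 at k = 1 because only the median is unbiased there.
- The share at 150 minutes is 31%, 50% and 64% by self-report, against 28% by Actigraphy.

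**Does the self-report re-run fill the gap?** Under Section 3.2, activity enters only the component that also requires 4% weight loss. Anyone losing 5% or more succeeds without it, anyone losing less than 4% cannot use it, and a qualifying A1C reduction makes it irrelevant. Only participants with 4% to under 5% loss who do not meet the A1C criterion can change status. The documents do not say how many that will be.

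**Feasibility of estimating bias.** The documents give no SD for the paired difference, so 60, 90 and 120 minutes/week are assumed, with 138 per arm and one averaged pair per participant.
- 95% CI half-width for bias in one arm, 1.96·SD/√138: 10, 15 and 20 minutes/week.
- 95% CI half-width for the between-arm difference in bias, 1.96·SD·√(2/138): 14, 21 and 28 minutes/week.
- Power for a 30-minute between-arm difference, two-sided 5%: 99%, 79% and 55%.

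Unmatched weeks would reduce this precision.

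**The case against.** The strongest reply is that correlation is not pinned down. No coefficient is named, and Section 3.1.6 is loose enough to list Actigraphy among self-report methods. A concordance coefficient, or an intraclass correlation for absolute agreement, does fall with bias, as the table shows. That much stands. But neither is named, and a single coefficient mixing bias with scatter still would not give the bias in minutes or the misclassification at 150.

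Second, Section 3.1.6 does not promise an estimate of reporting error by arm. Section 3.3 raises the arm difference to explain why self-report is not used alone, and Actigraphy in the primary endpoint is the protocol's answer. This also stands. Reporting by arm is an addition, suggested by the protocol's own warning.

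Third, the re-run of the primary endpoint does use the 150-minute cut-off and shows both arms under both measures. It would be wrong to say that nothing bears on the cut-off, or that the cut-off generally decides success. The look is indirect and does not estimate reporting error.

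Fourth, monthly survey and Actigraphy data are scheduled in both arms, so agreement could be computed later. A reader might infer that the trial cannot answer its validation question. The documents do not support that: the data will exist, and what is missing is a pre-specified analysis that uses them.

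Finally, the illustration's constant factor leaves r unchanged by construction. Over-reporting that varied between people would generally alter r, though r would still not measure the bias.

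**Conclusion.** The point holds as an improvement that should be made to a secondary objective. Following the stated method, the trial would not estimate the over-reporting that motivates the validation, its effect around 150 minutes/week, or whether it differs by arm. The invariance is exact. The sizes in the table rest on assumed distributions that no figure in the documents supports, so they show what is possible and do not predict this trial's data.

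Two stronger readings are tempting. One is that the primary comparison is compromised. It is not, because Sections 1.1 and 3.2 use Actigraphy there. The other is that a high correlation would be declared a validation however large the bias. The documents set no threshold or decision rule, and both Sections 3.1.6 and 3.3 show that over-reporting is already expected.

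**What to change.** In Sections 3.1.6 and 3.3, make agreement the validation measure, and add the method to Section 9.4.8:

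- Paired mean difference (self-report minus Actigraphy) with 95% limits of agreement. Use the log or ratio scale if the difference grows with level, with a stated rule for zero minutes. Either average to one value per participant or allow for repeated pairs.
- Sensitivity, specificity and percent agreement for reaching 150 minutes/week, with Actigraphy as the reference.
- Correlation kept as descriptive only.

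Before this is workable, three things must be settled:

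- Take Actigraphy minutes at the intensity the survey asks about, so that a difference in definition is not counted as reporting error.
- Reconcile the survey timing in Sections 8.2.4 and 11.6, and pair only matching weeks.
- Report results by arm, with the between-arm difference in bias and its confidence interval, for the study-team survey only. Minutes reported by the hDPPs exist in one arm and can be compared with Actigraphy only within it.

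The cost is revised wording, a modest amount of extra analysis and the loss of unmatched weeks. No added visit or measurement is needed.
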